8.10 Interim analysis

Formal interim analyses for efficacy will be performed twice: at the end of each enrolling season before the final analysis (which will occur at the end of the third enrolling season of 2019-2020) using the Lan-DeMets type I error spending function approach according to the O'Brien-Fleming group sequential method (Lan and DeMets, 1983; O'Brien and Fleming, 1979). The following table shows the O'Brien-Fleming group sequential boundary based on the design assumptions:

End of Enrolling Season Analysis	Information Fraction	Number of Primary Endpoint Events	Upper Efficacy Boundary	Nominal p-value
2017-2018	0.259	336	4.25	<0.0001
2018-2019	0.599	776	2.67	0.0075
2019-2020	1.000	1,296	1.98	0.0476

The Lan-DeMets approach allows flexibility needed in interim analysis of time to event data by using information time rather than calendar time to calculate the amount of type I error probability to spend at each interim analysis. Information time is defined as the number of accumulated events at interim analysis divided by the 1,296 events expected in the trial.

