## APPENDIX A

### Contemporary Heart Failure and Myocardial Infarction Trials/Cohort Studies Cardiovascular Event Rates

Trial/Registry	Cohort Treatment Arms	Eligibility	Endpoint	Event Rate (%)	Duration of Follow-up, months (Mn/Md)	Annualized Event Rate
SHIFT	HF Ivabradine Placebo	Age ≥18, stable NYHA II-IV any cause HF, LVEF ≤35%, sinus rhythm HR ≥70, hospitalized for HF w/in previous year, on stable background treatment	CV Death, HF Hosp.	28.7	22.9	15.0
			CV Death, HF Hosp., MI Hosp.	34.4		18.0
			CV Hosp.	30.0		15.7
BEAUTIFUL	Ischemic HF Ivabradine Placebo	Age ≥55 (or ≥18 if DM), established CAD, NYHA I-III HF, LVEF <40%, sinus rhythm, on stable background treatment	CV Death, HF Hosp., MI Hosp.	15.3	19	9.7
EPHESIS	Post MI LVD Eplerenone Placebo	Age ≥18, 3-14 d post-MI, NYHA II-III HF, LVEF ≤40% (if DM NYHA I)	CV Death, CV Hosp.	26.7	16	20.0
PARADIGM-HF	HF Sacubitril/valsartan Enalapril	Age ≥18, NYHA II-IV any cause HF, LVEF ≤40%, HF Hosp. within prior year and elevated NPs	CV Death, HF Hosp.	26.5	27	11.8
			CV Hosp.	31.9		14.2
ATLAS-ACS 2	Post-ACS Rivaroxaban Placebo	Age ≥18, 7 d post-ACS (if <55y needed also DM or prior MI)	CV Death, MI, Stroke	10.7	13	9.9
REACH (registry)	Prior Ischemic Event	Age ≥45 with any prior ischemic event (CAD, Cerebrovasc, PAD)	CV Death, MI, Stroke, Ischemic Hosp. (not incl. HF)	29.9	48	7.5
	Recent (<1y) Ischemic Event	Age ≥45 with ischemic event within past year		36.0		9.0
PEGASUS	Prior MI Ticagrelor Placebo	Age ≥50, prior MI 1-3 yrs + 1 additional risk factor	CV Death, MI, Stroke	9.0	36	3.3

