7. STUDY COHORT AND SAMPLE-SIZE JUSTIFICATION

The enrollment target is 4,650 subjects per treatment arm, for a total of 9,300 subjects. The assumed treatment effect size of high-dose vs. standard-dose influenza vaccine is derived from our meta-analysis of randomized trials of relatively healthy outpatients comparing these two active vaccination treatments, with an estimated risk reduction of 27% for the composite endpoint. After conservatively diluting the treatment effect among those with active heart disease by 35%, treatment with high-dose influenza vaccine is expected to result in an 18% risk reduction, i.e., a hazard ratio of 0.82, in all-cause death or cardiovascular hospitalizations, with an anticipated similar magnitude for all-cause death and cardiopulmonary hospitalizations. Based on data from contemporary clinical trials of patients with coronary heart disease or heart failure [1-9] the event rate for the primary endpoint is estimated to be 9% during the subject's 1st enrolling season following randomization for each subject, reducing to 8% during each subject's 2nd enrolling season, and 7% during each subject's 3rd enrolling season after vaccination, with 30% of the primary composite endpoint being death and 70% being cardiopulmonary hospitalization. Considering a follow-up to the end of summer phone call on July 31 (before the next influenza season) and a conservative 30% rate of not being vaccinated in each subsequent influenza season, a trial of 9,300 subjects with 500 subjects for the Vanguard year in 2016-2017 and 2,933 new subjects in each of the three influenza seasons in 2017-2018, 2018-2019 and 2019-2020 is projected to result in 45, 291, 440 and 519 primary endpoint events by the end of the 2016-2020 enrolling seasons for a total of 1,296 events. Assuming two interim analyses for efficacy using the O'Brien-Fleming group sequential method at the end of 2017-2018 and 2018-2019 influenza seasons, the trial will have power of 0.943 to detect an 18% risk reduction or power of 0.913 to detect a 17% risk reduction at a two-sided significance level of 0.05.

If proportion not vaccinated in each subsequent season is 20%, the trial will have power of 0.954 and 0.929 to detect a risk reduction of 18% and 17%, respectively. On the other hand, if proportion not vaccinated in each subsequent season is 40%, the trial will have power of 0.929 and 0.896 to detect a risk reduction of 18% and 17%, respectively.

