8.11 Multiple Endpoints and Testing

The type I error probability for the primary efficacy endpoint will be 0.05, two-sided. For all other analyses, two-sided p-values < 0.05 will be considered statistically significant with the number of comparisons made noted.

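### Interim information time uses a fixed 1,296 events although the final analysis is set by calendar, so higher event rates than planned would shift alpha to the second look and shrink the final threshold.

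*SAP*

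**What the plan says.** SAP 8.10, with the same rule in Protocol 13.11, sets the looks by season: "Formal interim analyses for efficacy will be performed twice: at the end of each enrolling season before the final analysis", the final analysis being one "which will occur at the end of the third enrolling season of 2019-2020". Boundaries are obtained "using the Lan-DeMets type I error spending function approach according to the O'Brien-Fleming group sequential method". For the interim looks, "Information time is defined as the number of accumulated events at interim analysis divided by the 1,296 events expected in the trial".

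The printed table gives 336, 776 and 1,296 events, fractions 0.259, 0.599 and 1.000, and boundaries 4.25, 2.67 and 1.98. It is introduced with "The following table shows the O'Brien-Fleming group sequential boundary based on the design assumptions". SAP 8.11 adds: "The type I error probability for the primary efficacy endpoint will be 0.05, two-sided".

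The 1,296 comes from SAP 7 and Protocol 13.12. There the "event rate for the primary endpoint is estimated to be 9" per cent in a subject's first season, then 8% and 7%, with 30% of events being deaths and 30% of subjects not revaccinated in each later season.

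Neither document says how the final critical value is set if the count at the end of 2019-2020 is not 1,296, or what happens if an interim look has already reached 1,296. SAP 6 gives July 31, 2019 as the data cut-off for the ITT analysis, one season before the final analysis in SAP 8.10.

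**The concern.** O'Brien-Fleming-type spending is chosen so that early looks are strict and the final test keeps almost all of the 0.05. That works when the denominator of the information fraction is close to the information that the final analysis will hold. Here the final analysis is fixed by date, so its information is whatever has accrued by then.

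If all season rates run above plan by the same factor, the true fraction at the end of 2018-2019 stays near 0.60, but events/1,296 rises towards 1 or past it. The second look then becomes lenient while a full season of data is still to come, and the last and most informative analysis is left with a very small threshold.

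A miss is plausible on the plan's own sources. In Protocol Appendix A ("Contemporary Heart Failure and Myocardial Infarction Trials/Cohort Studies Cardiovascular Event Rates"), the rows with broader endpoints in recent-heart-failure and post-infarction cohorts run from 14.2 to 20.0 per year. Over an assumed 8 to 10 months at risk this is 14.2 × 8/12 = 9.5% to 20.0 × 10/12 = 16.7%, before adding the non-cardiovascular deaths and pulmonary admissions that count here. Rows with narrower endpoints are lower (3.3 to 11.8 per year), so a shortfall is also possible.

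**Working it through.** **Inputs.** Accrual 500 + 3 × 2,933; season rates 9/8/7%; 30% of events are deaths; 30% not revaccinated; HR 0.82; 1:1 allocation (SAP 3 and 7). Two-sided alpha 0.05 (SAP 8.11). Information time at interim looks = events/1,296 (SAP 8.10).

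**Step 1: reproduce the projection.** A cohort's second-season events are n × (1 − 0.3 × 0.09) × 0.70 × 0.08. Third-season events multiply the number still in the trial again by (1 − 0.3 × 0.08) × 0.70, with rate 0.07.
- 2016-17: 500 × 0.09 = 45.0
- 2017-18: 264.0 + 27.2 = 291.2
- 2018-19: 264.0 + 159.8 + 16.3 = 440.1
- 2019-20: 264.0 + 159.8 + 95.5 = 519.3

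The total is 1,295.6, against 1,296 stated.

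**Step 2: reproduce the boundaries.** Spending per side is α(t) = 2[1 − Φ(z/√t)] with z = 2.2414 (the 0.9875 normal quantile), doubled for two sides. At t = 0.599 cumulative two-sided alpha is 0.0075. Solving by recursive numerical integration gives 4.249 / 2.672 / 1.981 and nominal p 0.00002 / 0.0075 / 0.0476, which matches the table. Power with information = events/4 is 0.945 at HR 0.82 (stated 0.943).

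**Step 3: scale the event rates (an assumption).** All three season rates are multiplied by one factor, with 30% non-return. Interim alpha is spent at events/1,296, the final look spends the remainder of 0.05, and correlations come from the actual counts.

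| First-season rate | Events at look 2 / final | Look-2 events/1,296 | Look-2 p threshold | Final p threshold | Power, HR 0.82 |
|---|---|---|---|---|---|
| 7% | 605 / 1,010 | 0.467 | 0.0021 | 0.0496 | 0.883 |
| 9% (plan) | 776 / 1,296 | 0.599 | 0.0075 | 0.0476 | 0.945 |
| 12% | 1,032 / 1,721 | 0.80 | 0.024 | 0.037 | 0.981 |
| 15% | 1,287 / 2,142 | 0.99 | 0.049 | 0.0042 | 0.978 |
| 18% | 1,540 / 2,560 | 1.19 | all 0.05 spent | none left | – |

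In counts, the second look reaches 1,296 at 1,296/776 = 1.67 times plan.

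**Step 4: same scenarios, denominator equal to the actual final count.** The second-look and final thresholds stay at about 0.0076 and 0.0476 in every row. Power at 15% is 0.996. The distortion therefore comes from the denominator.

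**Step 5: total error.** With the remainder spent at the final look, overall type I error is 0.0500 in every scenario where look 2 has not reached 1,296. If interim boundaries followed events/1,296 and the tabulated 1.98 were then reused at the final look, it would be 0.059 at 12% and 0.077 at 15%.

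**Step 6: the plan's own range.** At 20% and 40% not revaccinated the final counts are 1,379 and 1,216. The final Z is 1.989 and 1.975; reusing 1.98 would give an overall error of 0.0509 and 0.0494.

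**The case against.** The strongest reply is that the Lan-DeMets method permits a prespecified planned maximum as denominator. It holds the overall error as long as the final look spends what is left with the actual correlations. That is correct, and it rules out several stronger readings.

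- **A reader might infer that the plan inflates type I error.** The documents do not support this. The definition applies to interim looks, the table gives the final look a fraction of 1.000, the table is labelled as resting on design assumptions, and SAP 8.11 fixes the error at 0.05. Nothing instructs the team to reuse 1.98. An overall error of 0.078 at an 18% rate would need all alpha spent at look 2 and then a further test at 1.98. Keeping all three tabulated boundaries under proportional drift gives 0.050.
- **A reader might infer a power loss when events fall short.** At a 7% rate, a final threshold of 0.022 and power of 0.81 arise only if events/1,296 (0.78) is also applied at the final look. With the remainder spent, power is 0.883.
- **The larger scenarios are far from plan.** The only drift range the documents give is 20-40% non-revaccination, where the effect is negligible. Vaccination runs into January and counting starts two weeks later, so late enrollees have about six months at risk. On that basis the broader Appendix A rows become 7.1% (14.2 × 6/12) to 10.0% (20.0 × 6/12).
- **High event counts bring high power.** At 15% the second look alone has cumulative power of 0.944.

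What remains is that the stated rule gives up O'Brien-Fleming strictness at the second look when events run high, and that the final-look rule has to be inferred because neither document states it.

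**Conclusion.** The point holds as a weakness in how alpha is divided between looks, not as a failure to control it. Against 0.0075 and 0.0476 planned, the second-look and final thresholds become 0.024 and 0.037 at a 12% first-season rate, and 0.049 and 0.004 at 15%. The power cost at 15% is about two points (0.978 against 0.996). At about 1.67 times the planned rate or more, no alpha is left for the final analysis. Nothing is lost when events fall short, provided the remainder is spent.

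These sizes assume proportional scaling of all season rates, 30% non-return, information proportional to events, and seasons treated as independent although the SAP uses a robust variance. How likely rates of 12% or more are cannot be settled from the documents, because Appendix A points both ways.

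The July 31, 2019 cut-off makes an explicit final-look rule more important. A reader might infer that the primary analysis also closes then, but SAP 6 attaches that date to the ITT analysis and SAP 8.10 still says 2019-2020. If the final analysis did fall there, with 776 projected events, spending all remaining alpha gives Z 1.96 and power 0.79 at HR 0.82. Reading the fraction as 0.599 gives Z 2.67 and power 0.54.

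**What to change.** In SAP 8.10 and Protocol 13.11:

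1. Before each interim look, re-project the events expected at the calendar final analysis from blinded pooled counts, and use that number as the denominator of information time.
2. State that the final analysis has information fraction 1 and spends all remaining alpha, with its boundary recomputed from the actual event counts and not fixed at 1.98.
3. Reconcile the July 31, 2019 cut-off in SAP 6 with the 2019-2020 final analysis in SAP 8.10.

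Declaring the trial complete once 1,296 events are reached is not recommended. It could end the trial a season early and without the last 2,933 planned subjects, which is a design change. It is also unnecessary once item 1 is in place.

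The cost is wording only, with no extra patients and no unblinding. The one small burden is that the denominator must be documented from blinded data before each unblinded look.

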8.11 Multiple Endpoints and Testing

The type I error probability for the primary efficacy endpoint will be 0.05, two-sided. For all other analyses, two-sided p-values < 0.05 will be considered statistically significant with the number of comparisons made noted.

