### 13.5 Analysis of Secondary Endpoints

Secondary endpoints will include total (first and recurrent) cardiopulmonary hospitalizations or all cause-death during the subject's entire study participation duration, the composite of cardiovascular death or cardiovascular hospitalization within each enrolling season, the composite of all-cause death or cardiopulmonary hospitalization across all enrolling seasons, and individual components of the primary endpoint, including time to all-cause death and time to

first occurrence of cardiopulmonary hospitalization. Time to composite endpoints and times to individual components of the composite endpoints will be analyzed similarly as the primary endpoint in Section 13.4 with individual components of the composite endpoints that are non-terminating events analyzed using methods for competing risks. Recurrent events analysis will be performed for recurrent non-terminating events across all enrolling seasons. For all analyses, two-sided p-values < 0.05 will be considered statistically significant. In addition, the rate of cardiopulmonary hospitalization with death as competing risk will be analyzed using nonparametric and semi-parametric analyses based on the mean frequency function defined as the marginal mean of the cumulative number of cardiopulmonary hospitalizations over time subject to a terminal event of death.

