4.2. Secondary Efficacy Endpoints

- 4.2.1. Total (first and recurrent) cardiopulmonary hospitalizations or all-cause death across all enrolling seasons
- 4.2.2. Time to first occurrence of cardiovascular death or cardiovascular hospitalization within each enrolling season
- 4.2.3. Time to first occurrence of all-cause death or cardiopulmonary hospitalization across all enrolling seasons
- 4.2.4. Time to first occurrence of individual components of the primary efficacy endpoint, i.e. cardiopulmonary hospitalization and all-cause death, within each enrolling season

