8.5.2 ITT Analysis

Analysis of the secondary endpoints in 4.2.1 and 4.2.3 will follow the standard methods for analysis of randomized controlled trials as described below.

Analysis of the secondary efficacy endpoint of the total (first and recurrent) number of cardiovascular hospitalizations and all-cause death across all enrolling seasons in 4.2.1 will be analyzed using the proportional rates model by Mao and Lin (2016). In addition, the rate of recurrent cardiopulmonary hospitalization with all-cause death as competing risk will be analyzed using nonparametric and semi-parametric analyses based on the mean frequency function defined as the marginal mean of the cumulative number of cardiopulmonary hospitalizations over time subject to a terminal event of all-cause death by Ghosh and Lin (2000 and 2003).

Because of the randomization-once strategy for subjects who remain in the trial for multiple seasons, this approach will allow us to test the hypothesis that a strategy of high-dose influenza vaccine over multiple seasons will be superior to standard-dose influenza vaccination over multiple seasons, without running the risk that re-randomization would dilute a potentially cumulative effect. To examine this hypothesis, analysis of the secondary efficacy endpoint of the time to the first occurrence of all-cause death or cardiopulmonary hospitalization across all enrolling seasons will be performed as a standard ITT analysis using Kaplan-Meier method for estimation of the survival function, log-rank test, and Cox proportional hazards regression analysis, both stratified by the natural stratification factor of randomization year.

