8.8 Subgroup Analysis

Many baseline characteristics are known to be prognostic or suspected to be confounders for the clinical outcomes in the study population with high-risk cardiovascular disease. They include age, sex, race/ethnicity, smoking status, obesity (BMI \geq 30), baseline CV risk group (AMI vs HF), diabetes, renal dysfunction, and use of statin and beta-blocker medications. Influenza season is also known to affect the clinical outcome. Internal consistency of the primary analysis will be assessed in subgroups defined by these and other baseline characteristics. Heterogeneity of efficacy will be assessed using interaction

tests of treatment by each of these baseline covariates and by influenza season. Any interaction test resulting in a heterogeneity p-value < 0.10 will be further evaluated for clinical plausibility of effect modification.

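### Secondary efficacy endpoints can each be called statistically significant at an unadjusted two-sided 0.05, with no testing order and no gate on the primary

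*SAP*

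**What the plan says.** SAP 8.11 has two sentences. The first protects the primary: "The type I error probability for the primary efficacy endpoint will be 0.05, two-sided". The second covers everything else: "For all other analyses, two-sided p-values < 0.05 will be considered statistically significant with the number of comparisons made noted". Protocol 13.13 matches it, and Protocol 13.5, on the secondary endpoints, says: "For all analyses, two-sided p-values < 0.05 will be considered statistically significant".

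SAP 4.2 lists four secondary efficacy endpoints:

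- 4.2.1: "Total (first and recurrent) cardiopulmonary hospitalizations or all-cause death across all enrolling seasons" (ITT)
- 4.2.2: "Time to first occurrence of cardiovascular death or cardiovascular hospitalization within each enrolling season" (mITT)
- 4.2.3: "Time to first occurrence of all-cause death or cardiopulmonary hospitalization across all enrolling seasons" (ITT)
- 4.2.4: the two components of the primary, cardiopulmonary hospitalization and all-cause death, analyzed separately (mITT)

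SAP 8.5.2 presents 4.2.3 as a hypothesis test: "this approach will allow us to test the hypothesis that a strategy of high-dose influenza vaccine over multiple seasons will be superior".

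Subgroups have their own rule in SAP 8.8: "Any interaction test resulting in a heterogeneity p-value < 0.10 will be further evaluated for clinical plausibility of effect modification".

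**The concern.** The second sentence of SAP 8.11 is a positive rule. It does not merely leave multiplicity unaddressed; it says what a p-value below 0.05 will be called. Nothing makes that label depend on the primary result, and nothing ranks the secondaries. Noting how many comparisons were made tells the reader about the multiplicity but does not limit it.

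The secondaries include the results most likely to be promoted after a neutral primary: the multi-season strategy comparison, the cardiovascular composite, total events and mortality. There is also an asymmetry. At the final analysis the primary needs a nominal p of 0.0476 because of the interim looks (SAP 8.10). Endpoint 4.2.3 is the same composite counted across seasons, and it needs only 0.05. At stake is whether a significant secondary in the trial report can be read as a confirmed finding.

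**Working it through.** **The plan's own figures first.** Inputs from SAP 7 and 8.10: 1,296 events, 1:1 allocation, hazard ratio 0.82 or 0.83, looks at information fractions 0.259, 0.599 and 1.

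- Boundaries: Lan-DeMets O'Brien-Fleming-type spending at one-sided 0.025 gives 4.25, 2.67 and 1.98, with nominal two-sided p of 0.00002, 0.0075 and 0.0476. These match the table.
- Power: the expected Z is (√1296 / 2) × |ln HR|. For HR 0.82 this is 18 × 0.1985 = 3.572, and Φ(3.572 − 1.981) = 0.944. The full group-sequential calculation gives 0.945, against 0.943 stated. For HR 0.83 it gives 0.916, against 0.913 stated.

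The primary test is therefore sound. The documents state no family-wise error for the secondaries, so there is nothing to reproduce there.

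**Number of tests.** Endpoints 4.2.1, 4.2.2 and 4.2.3 give one test each and 4.2.4 gives two, so k = 5. This is a minimum: SAP 8.5.2 adds further analyses of recurrent hospitalization.

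**Independent tests.** 1 − 0.95⁵ = 0.226.

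**Correlated tests.** The endpoints share events, so their test statistics are positively correlated. The documents do not say how strongly, so a common correlation ρ is assumed and varied. With U standard normal and c a two-sided critical value, define

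A(U, c) = Φ((c − √ρ U)/√(1−ρ)) − Φ((−c − √ρ U)/√(1−ρ)).

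- At least one false-positive secondary: 1 − E[A(U, 1.96)⁵].
- Negative primary and at least one significant secondary, with the primary given the same ρ and judged at its final boundary 1.981: E[A(U, 1.981)] − E[A(U, 1.981) × A(U, 1.96)⁵].
- At least one false claim favoring high dose: 1 − E[Φ((1.96 − √ρ U)/√(1−ρ))⁵].

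| Assumed ρ | Any false-positive secondary | Same, with a negative primary | Favoring high dose only |
|---|---|---|---|
| 0 | 22.6% | 21.5% | 11.9% |
| 0.5 | 18.3% | 15.8% | 9.1% |
| 0.7 | 14.8% | 11.5% | 7.4% |
| 0.8 | 12.7% | 9.0% | 6.4% |
| 0.9 | 10.2% | 6.0% | 5.1% |

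Check of the first row: 0.2262 × (1 − 0.0476) = 0.215, and 1 − 0.975⁵ = 0.119.

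Counting 4.2.4 as one test (k = 4) lowers the first column to 18.5% at ρ = 0, 15.6% at 0.5 and 9.4% at 0.9.

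**Effect of control.** As a reference, Bonferroni at 0.01 per test gives 4.9% at ρ = 0 and 4.2% at ρ = 0.5.

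**The case against.** The best defense is that this is an explicit, prespecified convention. One primary endpoint carries the alpha, the secondaries are named as secondary, and the number of comparisons will be reported, so a careful reader can discount accordingly. Neither document promises family-wise control beyond the primary, so this is not a contradiction or a calculation error. That stands. It does not answer the wording: a report that follows the SAP would call such a result statistically significant even after a failed primary.

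Four stronger readings are tempting, and the documents do not support them.

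- **A single error rate.** A reader might settle on 16% to 18%. With five tests that requires a common correlation of about 0.52 to 0.64, which the documents do not give. The endpoints overlap heavily, so the upper end of the range is unlikely. An inflation of more than three times 5% also fails at a correlation of 0.7 and above.
- **A missed 5% target.** A reader might infer that the plan intended 5% for the secondaries and missed it. It never sets such a target; 5% is only an outside benchmark.
- **All of it as false claims for high dose.** The main figures count both directions. Claims favoring high dose run from 5.1% to 11.9%, against a one-sided 2.5% for a single test.
- **The subgroup tests.** A reader might extend the point to the ten named factors plus season. About 11 × 0.10 = 1.1 chance flags are expected there, and with independent tests the chance of at least one is 1 − 0.9¹¹ = 0.69. The general 0.05 sentence could literally reach these tests. However, SAP 8.8 uses subgroups to check consistency of the primary result, and a flag triggers only a plausibility review. That is a chance of a review, not of a false claim.

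The endpoints in SAP 4.5 and the analysis in 8.3.3 are already headed exploratory, so the missing label matters mainly for the secondaries.

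**Conclusion.** The point holds for the secondary efficacy endpoints. As written, any of them can be declared significant at a full two-sided 0.05 whatever the primary shows. Under the global null, with five tests and a common correlation between 0.9 and 0, at least one false-positive secondary occurs in about 10% to 23% of trials, and alongside a negative primary in about 6% to 21.5%. The range rests on an assumed equal correlation. Even at 0.9 the two-sided rate is about twice 0.05. The primary type I error and power are untouched, so this is a cheap improvement to how secondary results may be described, not a flaw in the main conclusion.

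**What to change.** Before unblinding, replace the second sentence of SAP 8.11 and align Protocol 13.5 and 13.13 along these lines:

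*The secondary efficacy endpoints are formally tested only if the primary efficacy test crosses its group-sequential boundary. They are then tested in a fixed order, each at two-sided 0.05, stopping at the first non-significant result. All other non-primary p-values, including those after a failed step, are nominal and will not be described as statistically significant.*

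The order is the sponsor's to choose and justify. The SAP numbering need not be followed, given the weight that SAP 8.5.2 puts on the multi-season hypothesis in 4.2.3. The list should name one test per endpoint or component. If the primary crosses early, testing a secondary at a full 0.05 at that look can exceed 5% by no more than about one percentage point under the stated boundaries, which does not call for a separate adjustment.

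A simpler acceptable alternative is to label all non-primary p-values nominal.

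The cost is wording only: no patients, no data, and no effect on the primary test or its power. The downside is that a secondary after a failed primary or a failed step can be reported only as nominal, however small its p-value. SAP 8.8 needs no change on this account.
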